1.1. Synopsis

Protocol Title:

European DisCoVeRy for Solidarity: An Adaptive Pandemic and Emerging Infection Platform Trial

Brief Title:

EU-SolidAct

[figure not shown]
Rationale and Overall Design:

There is an urgent need for developing an adaptive pan-European research platform for rapid and coordinated investigation of new candidate drugs during ongoing pandemics. EU-SolidAct is an Adaptive Platform Trial master protocol developed for evaluating drug interventions in hospitalized patients with COVID-19. While this master protocol is developed for therapeutic interventions in hospitalized patients, it could also form the basis for trial protocols on other interventions and/or in non-hospitalized populations. The protocol is, additionally, developed to facilitate a joint European response to the challenge of evaluating interventions during future epidemics. The described disease states and endpoints may need to be adapted to the epidemic in question.

EU-SolidAct is a European, multicentre, randomized, parallel, phase 2 and 3 platform trial on drug interventions, both new and repurposed, single or in combination, in hospitalized adult patients with moderate or severe COVID-19, as defined by the WHO Working Group on the Clinical Characterisation and Management of COVID-19¹. Participants with moderate disease (WHO score 4-5) will be eligible for EU-SolidAct Part A, whereas participants with severe/critical disease (WHO score 6-9) will be eligible for EU-SolidAct Part B. This might include participants progressing from Part A.

In Part A of phase 3 confirmatory trials, the primary objective is to determine the effect of *therapeutic interventions* on occurrence of disease progression, from moderate disease to severe/critical disease or death within 14 days. In Part B, the primary objective is to determine the effect of *therapeutic interventions* on occurrence of death within 60 days.

[figure not shown]
In phase 2 the default objective for both parts is to explore the effect of the therapeutic intervention on respiratory dysfunction at day 5. Other objectives, e.g. effect on virological outcomes may be considered based on the treatment mode of action.

EU-SolidAct Master Protocol version 2.2

In addition to single treatments, combination of treatments could also be assessed through factorial design. EU-SolidAct is designed to be adaptive and to enable inclusion of hospitals in Europe and beyond, regardless of epidemic waves and available resources. This requires the master protocol to be modular, ranging from a core set of outcomes to more advanced data capture. Hospitals will access the study on different pre-set levels, ranging from a core set of clinical endpoints and safety measures, to a more advanced level with biobanking and possibilities for add-on studies.

- Level I commitment is set as the minimum requirement for participation. This level includes a core set of clinical endpoints, safety measures and patient reported outcome measures (PROMs) to enable a maximum inclusion rate of eligible patients. These measures are developed in close dialogue with regulatory authorities to ensure that data collection is sufficient to allow for marketing authorization of drugs to be tested. The required data collection will depend on the drugs being tested.

- Level II commitment is strongly preferred and intended for hospitals with resources available for biobanking at time of inclusion. Biobanking is necessary to assess virological endpoints.
- Level III is intended for hospitals that can participate on a more advanced level. Level III participation enables further scientific questions to be explored, by including e.g. advanced biobanking, pharmacokinetics/dynamics, imaging, organ-related short and long-term outcomes and expanded collection of PROMs. Which outcomes to include would depend on the scientific interest of the participating hospitals, allowing for add-on studies in selected sites, with shared standardised protocols. An additional opportunity for Level III is to identify patient characteristics and biomarkers that aim to predict treatment responses and can lay the foundation for personalized treatment options. Follow-up may be extended beyond 90 days.

The level of complexity can be modulated depending on the scale of the pandemic at a given period, and a participating hospital can request to change between the levels during phases of the pandemic, as participation may depend on available resources.

Brief Summary:

The overall aim of EU-SolidAct is to evaluate the safety and efficacy of therapeutic agents in hospitalized patients diagnosed with SARS-CoV-2, to reduce overall mortality and morbidity, as well as burden of disease on the health systems.

General master study details include:

EU-SolidAct Master Protocol version 2.2

- The study duration will be up to 90 days (± 14 days) for each participant.
- The treatment duration will be defined in the investigational-specific subprotocols.
- The assessment frequency:
 - Participants will be screened, assessed for eligibility and enrolled as soon as possible after admission.
 - Baseline assessments and randomization at Day 1 as soon as possible after screening.
 - Day 3, 5, 8 (± 1 day) assessments during hospitalisation, then weekly visits until discharge (Day 15 ± 3 , Day 22 ± 3 , Day 29 ± 3 , etc.).
 - Assessments at Day 15 ± 3 , Day 29 ± 3 , Day 61 ± 7 (end points) and Day 91 ± 14 (end of study) will be done at hospital (if participants are still hospitalized); or in the outpatient setting or by phone (if participants are discharged from hospital).
- Number of enrolled Participants:
 - For phase 3 *superiority trials* approximately 1000 participants will be screened to achieve 950 randomly assigned to each arm in Part A and approximately 1000 participants will be screened to achieve 950 randomly assigned to each arm in Part B. For phase 3 *non-inferiority trials*, about 3000 in each arm is needed. For phase 2 trials, about 200 in each arm will be included.
 - Where combination therapies are assessed by factorial design, the main assumption will be that no interaction exists between the treatments and therefore no modification of the sample size will be planned. If synergies or effect modifications between treatments are of interest, the intervention-specific sub-protocols will define the sample size needed for detecting the interaction effect.

Note: *Enrolled* means a participant, or his/her legally authorised representative, has provided informed consent to participate and has been screened and found eligible for the trial. The participant will *not* be considered enrolled if the informed consent has been withdrawn prior to participating in any other study activity than screening.

- Intervention Groups and Duration:
 - Detailed in the intervention-specific sub protocols.
- Data Monitoring:
 - A data monitoring committee has been appointed for this study. The data monitoring committee is a group of independent scientists who are appointed to monitor the safety and scientific integrity of a human research intervention, and to make recommendations to the sponsor regarding the stopping of an intervention for harm or for futility. The composition of the committee is based on the scientific skills and knowledge required for monitoring the particular study. There will only be one data monitoring committee overseeing all trial arms.

1.2. Schedule of Assessments (SoA)

Procedure	Screening	Baseline	Assessments during hospitalisation	Primary endpoint Part A	Core secondary end point	Primary endpoint Part B	End of study/Early withdrawal
Day ± window		1	Day 3, 5, 8 (all ±1 day), then weekly (±3 d), or until discharge	15±3	29±3	61±7	91±14
Screening for eligibility¹							
Review SARS-CoV-2 laboratory results	X						
Informed consent	X						
Allocation to EU-SolidAct Part A or B by WHO disease stage ²	X						
Baseline procedures							
Demographics and medical history	X	X					
Randomization		X					
Standard of care (SoC) ³		X					
Study intervention		X	Note doses given				
Safety laboratory							
Safety biochemistry ⁴	X	(X)	X	X ⁵	X ⁵	X ⁵	X ⁵
Pregnancy test		X					
Study procedures							
Vital signs including SpO ₂		X	X	X ⁵	X ⁵	X ⁵	X ⁵
Review oxygen therapy ⁶		X	X	X ⁵	X ⁵	X ⁵	X ⁵
Review WHO stage ⁷		X	X	X ⁵	X ⁵	X ⁵	X ⁵
Concomitant medication		X	Note changes daily until discharge, note on occurrence	X ⁵	X ⁵	X ⁵	X ⁵
AE and SAE evaluation				X ⁵	X ⁵	X ⁵	X ⁵
PROM							X
Endpoints assessment							
Endpoint assessment ⁸		X	X	X	X	X	X
Biobanking (level II)							
Serum, EDTA Plasma, Whole blood		X	Day 3, 8, 15, 22 (all ±1) or until discharge before D22				
Naso/oropharyngeal swab		X	Day 3, 8, 15 (all ±1) or until discharge before D15				
Add-on studies (level III)							
Biobanking, other material		X	Add-on sub protocols				
Radiology		X	Add-on sub protocols				
Organ function		X	Add-on sub protocols				
PROM		X	Add-on sub protocols				

Modular data capture according to level of commitment (level I, level II, level III). Assessments in level I are mandatory. Biobanking (level II) is necessary for virological end points. Add-on sub-studies (level III) will be developed in collaboration with participating sites, developing common standardised procedures for additional biobanking, radiology and organ function.

1. Refer to chapter 8 for details. Screening/baseline assessments should be performed prior to study drug administration.
2. See separate table 4.1 for WHO stage and allocation to EU-SolidAct Part A (moderate disease) or B (severe disease).
3. Standard of Care (SoC) details, including medication.
4. The following laboratory results should be collected: Hb, leukocytes, lymphocytes, neutrophils, platelets, sodium (Na), potassium (K), creatinine, glucose, total bilirubin, INR, ALT, AST, amylase, LDH, D-dimer, CRP, procalcitonin, ferritin. Repeat at baseline if >24 h since screening. If not, enter laboratory results from screening. If ferritin and procalcitonin are not routinely gathered at a site for clinical follow-up, these analyses should be prioritized at baseline, D8 and D15.

5. If still hospitalized. At discharge or early discontinuation, register WHO disease progression scale, review concomitant medication and adverse events as detailed in section 8.
6. Specify oxygen therapy: a) Nasal prongs, b) Face mask, c) Face mask with reservoir, d) High flow oxygen e) Non-invasive ventilation (NIV) f) Mechanical ventilation/Extracorporeal membrane oxygenation (ECMO) Enter numbers of litres of O₂ provided or fraction of inspired O₂ (FiO₂), unless on ECMO
7. Review WHO stage including mode of oxygen therapy for end point assessment (progression on WHO scale)
8. If discharged, endpoint assessments including sustained recovery, will be conducted by telephone contact with the patient and/or by reviewing patient records and/or contacting primary caretaker and/or relatives.

2. Introduction

2.1. Study Rationale and Background

The novel SARS-2 Coronavirus (SARS-CoV-2) was identified in December 2019 as a cause of severe pneumonia, acute respiratory distress syndrome (ARDS) and potential multiorgan failure in humans. The disease known as COVID-19 has since escalated into a pandemic affecting nearly all countries in the world where it has caused widespread mortality and morbidity.

There is a pressing need for large scale testing of repurposed and novel agents to provide new treatment options for patients with COVID-19. This testing will be facilitated in an Adaptive Platform Trial master protocol. The protocol EU-SolidAct is developed in collaboration with relevant stakeholders including the European Medical Agency (EMA).

EU-SolidAct is a multicentre/multi-country trial aiming to include hospitalized patients at academic and non-academic centres in Europe and beyond, regardless of epidemic waves and available resources. This requires the master protocol to be modular, ranging from a core set of outcomes to advanced data capture described in the protocol as levels I, II and III. The sponsor is Oslo University Hospital (OUH) and the study is funded by the European Union's Horizon 2020 research and innovation program.

The study will compare different investigational therapeutic agents plus standard of care (SoC) to SoC possibly in combination with matching placebo. There will be interim analyses to allow early withdrawal of therapeutic agents that show a suboptimal adverse event profile, and to allow for continuous monitoring of the futility of included drugs. While this master protocol is developed for drug interventions in hospitalized patients, it should be feasible to expand the protocol to other interventions and/or to non-hospitalized patients. Importantly, the protocol is developed so that it could form the basis of a joint European response to evaluating interventions in future epidemics.

2.2. Benefit/Risk Assessment

General risk/benefit assessment (excluding intervention-specific risk/benefit):

Participants in this study will be exposed to few general risks beyond being hospitalized. Through bio-banking, the participants will be subjected to additional blood sampling which should be of little inconvenience. Collection of other samples, like oropharyngeal or nasal swabs, can give some transient discomfort.

Participants' identities will be protected, and personal health information (PHI) held securely. No directly identifiable data will be stored in the clinical trial database, and the participant lists will be stored separately, secured, at the local study sites. The risk that unauthorized persons will see the participant's PHI will be kept at a minimum, and measures will be taken to keep PHI confidential and in accordance with the legal requirements.

Specific risk/benefit assessment:

Specific risk/benefit assessments are described in the intervention-specific sub-protocol in alignment with the Investigator's Brochure (IB) and Summary of Product Characteristics (SmPC) for the specific intervention. The severity of the disease (moderate/severe) will be decisive when the risk/benefit assessment is performed. Importantly, enrolled participants may develop critical illness and the implementation of a new drug in this situation may induce unknown effects that may aggravate organ dysfunction.

3. Objectives and Endpoints

3.1. Phase 3 Trial Objectives and Endpoints

In phase 3 confirmatory trials, the primary objectives and endpoints are described below. Secondary objectives and endpoints as listed below should be considered for all interventions studied within this platform. The final selection and any additional intervention-specific objectives or endpoints will be described in corresponding sub-protocols.

Table 3.1 Phase 3 objectives and corresponding endpoints

Objectives	Endpoints
Primary	
Part A, moderate disease	
The primary objective is to determine the effect of therapeutic interventions on occurrence of disease progression in hospitalized patients with moderate COVID-19	Occurrence of disease progression, defined as a progression of disease state from moderate (WHO score 4-5) to severe/critical (WHO score 6-9) or death (WHO score 10) within 14 days
Part B, severe disease	
The primary objective is to determine the effect of therapeutic interventions on occurrence of death in hospitalized patients with severe or critical COVID-19	Occurrence of death within 60 days
Secondary	
Secondary objectives are 1. to determine the effect of therapeutic interventions on other clinical endpoints	1.1 Occurrence of disease progression, defined as a progression of disease state from moderate (WHO score 4-5) to severe/critical/death (WHO score 6-10) or from severe/critical (WHO score 6-9) to death within 28 days 1.2 Time from randomization to sustained recovery, defined as being discharged from the index hospitalization, followed by being alive and at home for 14 consecutive days within 90 days

	
1.3 Time from randomization to first hospital discharge within 90 days
 
1.4 Disease state on a 5-point scale defined as:
 
 1. Mild (WHO score 1-3) or better, 2. Moderate (WHO score 4-5), 3. Severe (WHO score 6), 4. Critical (WHO score 7-9) or 5. Death at Day 15 and 29 
1.5 Time from randomization to recovery defined as no need for oxygen
 
1.6 SpO₂/FiO₂-ratio at day 3, 5 and 8

2. to determine the effect of therapeutic interventions on viral clearance	2. Viral clearance as assessed by SARS-CoV-2 PCR in oropharyngeal specimens during hospitalization
3. to determine the effect of therapeutic interventions on biochemical parameters	3. Biochemical parameters including inflammatory markers (C-reactive protein, ferritin, lactate dehydrogenase, procalcitonin, D-dimer, leukocyte subsets and cytokine panels) during hospitalisation
4. to assess the safety impact of therapeutic interventions on major serious adverse events	4. Occurrence of serious adverse events leading to study treatment discontinuation or death
5. to determine the effect of therapeutic interventions on patient reported outcomes	5. The Oslo COVID-19 QLQ-PW80 subscale scores at Day 91

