4.4. End of Study Definition

Participant Completion

A participant is considered having completed the study if he/she has completed all periods of the study including the last scheduled procedure at Day 91 shown in the Schedule of Assessments (SoA, section 1.2). The expected total trial duration for each participant will be approximately 90 days. If longer or shorter duration is warranted to meet the objectives of specific investigations, this will be stated in the corresponding sub-protocol.

Intervention-Specific Completion

The study of a specific intervention is considered completed when the last participant in the intervention cohort has completed all periods of the study including the last scheduled procedure shown in the SoA.

Platform Study Completion

The platform is considered completed when the last intervention-specific study has been completed.

5. Study Population

All participants must satisfy all the inclusion and exclusion criteria in this master protocol to be enrolled in the platform trial. Any additional intervention-specific criteria will be described in the applicable sub-protocol. The eligibility criteria will be considered by the principal investigator or delegated clinical site personnel.

Prospective approval of protocol deviations to recruitment and enrolment criteria, also known as “protocol waivers” or “exemptions”, are not permitted.

The eligibility criteria listed below are quite general and is suited for phase 3 confirmatory trials. In phase 2 exploratory trials, more restrictive criteria might be necessary to accommodate the increased uncertainty and potential risk of the treatment.

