8.6.1. Time period and frequency for collecting AE and SAE information

- All AEs and SAEs will be collected from the signing of the informed consent form (ICF) until the follow-up visit at the time points specified in the SoA (section 1.2.).
- Except disease-related events as defined in section 8.6.9. and exceptions mentioned above, all SAEs will be recorded and reported to the sponsor and the delegated designee, Inserm-ANRS Pharmacovigilance Office, immediately and under no circumstance should this exceed 24 hours, as indicated in the trial Safety Management Plan (SMP). The investigator will submit any updated SAE data within 24 hours of it being available.
- Investigators are not obligated to actively seek information on AEs or SAEs after conclusion of the study participation. However, if the investigator learns of any SAE, including a death, at any time after a participant has been discharged from the study, and he/she considers the event to be reasonably related to the study intervention or study participation, the investigator must promptly notify the sponsor and the delegated designee, Inserm-ANRS Pharmacovigilance Office.

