9.3.5. Safety analyses

Safety endpoints include serious adverse events (SAEs) leading to study treatment discontinuation and death. SAEs will be coded using the current version of the Medical Dictionary for Regulatory Activities (MedDRA). SAEs leading to study treatment discontinuation and death will be summarized with number and proportion. More details on the statistical analysis will be provided in the SAP.

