- Systemic inflammation during hospitalization

Overall Design:

Double blind, multicentre, randomized, placebo-controlled trial (RCT)

Number of Participants enrolled:

Approximately 2000 participants will be screened to achieve 1900 randomly assigned to baricitinib or placebo to end up with 1848 evaluable participants (924 per arm).

Intervention Groups and Duration:

- 4mg Baricitinib up to 14 days + SoC
- Matching placebo up to 14 days + SoC

The study duration will be up to 90 days (\pm 14 days) for each participant. Baricitinib and placebo will be provided for up to 14 days, as long as the patient is hospitalized.

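### Endpoint 4, the only safety endpoint the protocol names, cannot count a non-fatal SAE once study treatment has ended; read as one composite, it lets fewer deaths offset added non-fatal harm

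*Protocol*

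**What the plan says.** Table 3.1 (section 3.1) links the safety objective, which concerns major serious adverse events, to a single endpoint: "Occurrence of serious adverse events leading to study treatment discontinuation or death". Section 9.3.5 restates it with a different conjunction: "Safety endpoints include serious adverse events (SAEs) leading to study treatment discontinuation and death". The summary planned there is "SAEs leading to study treatment discontinuation and death will be summarized with number and proportion". The Bari-SolidAct synopsis in 10.8.1 lists the Table 3.1 version and no other safety endpoint.

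Treatment length is left open at platform level: "The treatment duration will be defined in the investigational-specific subprotocols". For Bari-SolidAct it is fixed: "Baricitinib and placebo will be provided for up to 14 days, as long as the patient is hospitalized".

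Follow-up is much longer (section 4.4): "The expected total trial duration for each participant will be approximately 90 days". Safety data run over all of it (section 8.6.1): "All AEs and SAEs will be collected from the signing of the informed consent form (ICF) until the follow-up visit", at the time points of the schedule of assessments, the last being Day 91. Section 8 also asks that readmissions found at the Day 15, 29, 61 and 91 contacts be reported as SAEs.

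Three other rules matter. The Part B primary endpoint is "Occurrence of death within 60 days", and section 8.6.8 requires an SAE declaration for every death. Section 8.6.9 keeps the disease-related events of Appendix 4 out of SAE reporting unless the investigator sees a reasonable possibility that the intervention caused them. Section 4.1 allows open-label comparison with SoC alone.

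**The concern.** The endpoint ties a non-fatal SAE to an action, stopping study treatment, that is possible only while treatment is being given. With a short course and long follow-up, most of the observation time contributes only deaths. Non-fatal harm that appears after the course, including any non-fatal readmission, is collected but cannot enter the endpoint.

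In an arm given SoC alone there is no study treatment to stop. The non-fatal part is then zero in that arm by definition and open to events in the active arm, so the comparison is not like with like. Bari-SolidAct has a placebo and escapes this problem; an open-label sub-protocol would not.

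If the endpoint is analysed as one composite, it also contains the deaths that form the Part B primary endpoint. An intervention that lowers mortality could then look neutral or favourable on safety while causing more non-fatal serious events. The safety objective would be answered largely by the efficacy result.

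**Working it through.** **1. The plan's own Part B figure.** Inputs from section 9.5.1 and Table 9.3: 15% vs 10% deaths, two-sided 5%, 90% power.
- HR = ln(0.90)/ln(0.85) = 0.648, as stated.
- The Freedman formula gives 231 events. With a mean event rate of (15% + 10%)/2 = 12.5%, 231/0.125 = 1848, or 924 per arm, as stated.
- The Schoenfeld formula gives 224 events, as stated.

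So 924 per arm and 15% vs 10% can be carried forward. The protocol gives no rate or power for the safety endpoint.

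**2. Time in which a non-fatal SAE cannot count (Bari-SolidAct).** Treatment starts on Day 1 and ends by Day 14; follow-up ends at Day 91. Days 15 to 91 are 77 days, and 77/91 = 0.846, about 85%. The share is larger for anyone discharged before Day 14. For other interventions it depends on the sub-protocol.

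**3. Offsetting within a composite.** Let D be the proportion who die and F the proportion who survive but have a non-fatal SAE leading to discontinuation. Counted this way the categories do not overlap, so the composite is D + F and its difference between arms is ΔD + ΔF. With the planned ΔD = 10% − 15% = −5 points, the composite difference is −5 + ΔF. It is zero or favourable for every ΔF up to +5 points, whatever the control value of F.

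The values of F below are assumptions: control 2% to 5%, increase 2 to 5 points. The last two columns give power to detect the harm when deaths are equal (normal approximation for two proportions, two-sided 5%, 924 per arm).

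| Non-fatal, control → intervention | Composite, deaths 15% vs 10% | Composite, deaths 15% vs 15% | Power, non-fatal alone | Power, composite |
|---|---|---|---|---|
| 2% → 4% | 17% vs 14% | 17% vs 19% | 0.71 | 0.20 |
| 2% → 5% | 17% vs 15% | 17% vs 20% | 0.94 | 0.38 |
| 2% → 7% | 17% vs 17% | 17% vs 22% | 1.00 | 0.77 |
| 5% → 7% | 20% vs 17% | 20% vs 22% | 0.44 | 0.18 |
| 5% → 8% | 20% vs 18% | 20% vs 23% | 0.74 | 0.35 |
| 5% → 10% | 20% vs 20% | 20% vs 25% | 0.98 | 0.73 |

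**4. One point inside that range, with intervals.** Take 2% → 6% and deaths of 15% vs 10%.
- Composite 17% vs 16%: SE = √(0.17×0.83/924 + 0.16×0.84/924) = 0.0173; difference −1.0 point (95% CI −4.4 to 2.4).
- Non-fatal alone: SE = √(0.02×0.98/924 + 0.06×0.94/924) = 0.0091; difference +4.0 points (95% CI 2.2 to 5.8).

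The same data would read as no difference on the composite and as clear harm on the non-fatal line.

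**The case against.** Much can be said for the plan. Section 9.3.5 says that safety endpoints *include* these events and leaves detail to the SAP. Section 3.1 lets sub-protocols add endpoints, and 10.8.1 is only a synopsis of one. Section 9.2 presents safety data from all observed data, AESIs are monitored over the whole follow-up (8.6.11), and the data monitoring committee reviews safety (9.4). A reader might infer that late harms go unrecorded or unreported, or that the benefit-risk conclusion must be wrong. The documents do not support that. What stands is narrower: the one safety endpoint the protocol does define is badly fixed, and its definition is not a detail left to the SAP.

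The *and* in section 9.3.5 can be read as two separate summaries, in which case nothing is offset. That reading is fair, but Table 3.1 and 10.8.1 say *or*, so the protocol does not settle it. Deaths are also analysed on their own as the Part B primary endpoint, so the fatal part would be visible; the non-fatal part would not.

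Three further inferences go too far. Fourteen days is a Bari-SolidAct figure, not a platform rule. The 15% vs 10% is 60-day mortality; the protocol gives no on-treatment mortality for Part B, and the offset is not confined to the treatment period because deaths count throughout. Stroke and pulmonary embolism are tempting examples of missed late SAEs, but both are in Appendix 4 and become SAEs only if causation is suspected. An any-SAE count would therefore also miss many of them.

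Finally, the objective concerns *major* SAEs. In severe or critical illness an any-SAE count carries much background morbidity, and it still contains death. That argues against simply replacing the endpoint with any SAE, not against showing the components.

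**Conclusion.** The point holds in this form and should be acted on. Two parts follow from the wording alone. After study treatment ends, endpoint 4 can count only fatal events; in Bari-SolidAct that covers at least 85% of study days. In an SoC-only arm the non-fatal part cannot occur.

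The third part is conditional. If the endpoint is analysed as one composite, a 5-point fall in deaths cancels a rise of up to 5 points in non-fatal SAEs leading to discontinuation. This rests on the planned 60-day mortality for Part B, on non-overlapping categories and on assumed non-fatal rates. It shows that the endpoint can mislead, not that it will. Even with equal deaths, power to detect the harm falls, for example from 0.94 to 0.38 for a rise from 2% to 5%. In Part A, where section 4.2 expects far fewer deaths, the offset is weaker.

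**What to change.** In Table 3.1, section 9.3.5 and section 10.8.1:

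- Keep SAEs leading to discontinuation of study treatment as one reported line. Reconcile *or death* with *and death* by stating that the components are reported separately.
- Add by-arm reporting, from first dose (from randomization in SoC-only arms) to Day 91, of (a) any SAE, (b) non-fatal SAEs with death as a competing event, and (c) death.
- Tabulate the Appendix 4 disease-related events by arm, since section 8.6.9 keeps them out of the SAE counts unless causation is suspected.

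No new data collection is needed: SAEs are collected to Day 91 and disease-related events are recorded in the eCRF. The cost is a change of wording and a few more tables. The downside is that any-SAE percentages will be higher and include background morbidity, which is why the discontinuation line should stay.
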